## **1** INTRODUCTION

## 1.1 Background

The methods and presentation of data analyses proposed for this study are described in detail in this Statistical Analysis Plan (SAP), in order to avoid post hoc decisions that may affect the interpretation of the statistical analysis.

This SAP is based on the analyses described in the protocol and the data actually obtained in the study. Any deviations from the methods in the protocol will be described and explained in section 3.12.

The preparation of this SAP was completed prior to unblinding of the study.

## 1.3 Compliance with Good Clinical Practice

This SAP is designed to ensure compliance with appropriate ICH guidelines, particularly E9 (Statistical Principles for Clinical Trials) and E3 (Structure and Content of Clinical Study Reports).

## 1.4 Work Policy (Standard Operating Procedures)

The following statistical Standard Operating Procedures (SOP) belonging to CroxxMed ApS will be followed during the conduct of the study:

- SOP for Statistical Protocol input, Analysis and Study Reporting
- SOP for Statistical Programming

## 1.5 Software and File Storage

The data will be processed within the SAS®/Windows environment. The statistical report will be written in Microsoft Office Word 2010.

Electronic documents will be protected with a study-specific password.

- Software: SAS®, version 9.4.

- Location: Original database at CroxxMed ApS, the study statistician will obtain copies. The study statistician will keep SAS programs during the conduct of the analysis.

## 1.6 Clean File

A Clean File meeting will be held just before closing the database for the final analysis. At this meeting, it will be decided which subjects will be included in the analysis(-es), and the database will be declared clean and accurate.

The randomization code can be broken after Clean File and entered/loaded into the database in accordance with the Clean File Protocol.

## **1.7 Backup and Recovery Procedures**

A system backup will be run every night, and the data will be stored in secure settings at a hosted server at the Electronic Data Capture vendor's premises.

## 1.8 Archiving

Electronic documents will be stored at CroxxMed during the conduct of the study. The original SAP (with signatures) will be filed in the Trial Master File once the study is closed. The Trial Master File will be in paper form, and electronic documents will be stored as a backup for a short period of time after study closure.

## 2 STUDY OBJECTIVE(S) AND DESIGN

## 2.1 **Objective(s) and Variables**

### 2.1.1 Primary Safety Objective

• To compare the safety of AP1189 against placebo by evaluating AEs, SAEs, and laboratory abnormalities.

### 2.1.2 Primary Safety Variables

AEs, SAEs, and laboratory abnormalities.

See section 3.6 for details of the calculation of primary safety variables.

### 2.1.3 Primary Efficacy Objective

• Effect of AP1189 vs. placebo in subjects with severe active RA (CDAI > 22), undergoing uptitration with MTX, by showing a change in CDAI from severe (CDAI > 22) to moderate or lower (CDAI ≤ 22) after 4 weeks treatment compared to baseline.

### 2.1.4 Primary Efficacy Variables

The change in CDAI after 4 weeks of treatment compared to baseline will be evaluated by assessing the following, by treatment group:

- Mean change in CDAI from baseline to week 4
- Proportion of subjects with a change in CDAI score from severe (CDAI > 22) to moderate (CDAI ≤ 22) at week 4 compared to baseline.

See section 3.6 for details of the calculation of primary efficacy variables.

#### 2.1.5 Secondary Efficacy Objectives

To compare the effects of AP1189 against placebo by assessing:

- Proportion of subjects achieving a reduction of more than 10 (ten) swollen and/or tender joints at week 4 compared to baseline
- Proportion of subjects achieving a change in CDAI score at week 4 compared to baseline
  - Proportion of subjects with a 5-point decrease
  - Proportion of subjects with a 10-point decrease
  - Proportion of subjects with a 15-point decrease
- Proportion of subjects achieving a change in value to ≤ 3.2 as measured by DAS28 at week 4 compared to baseline

Study SynAct-CS002 – Statistical Analysis Plan

- Change in subject-reported HAQ-DI at week 4 compared to baseline
- Change in subject-reported fatigue using FACIT-Fatigue at week 4 compared to baseline
- Proportion of subjects achieving American College of Rheumatology (ACR) response assessed by ACR20, ACR50, and ACR70

#### 2.1.6 Secondary Efficacy Variables

The secondary efficacy variables are described in 2.1.5 above, with the following addition:

• The number of swollen and/or tender joints are found by summarizing SJC and TJC.

See section 3.6 for details of calculation of secondary efficacy variables.

### 2.1.7 Tertiary Efficacy Objectives

Effect of AP1189 compared to placebo at week 4 compared to baseline on inflammatory and collagen destructive biomarkers. The biomarkers include:

- CXCL13
- IL-1β
- IL-6
- IL-10
- TNF-α

### 2.1.8 Arthroscopy sub-Study

Effect of AP1189 compared to placebo on joint structures and inflammation as assessed by synovial biopsy at baseline and after 4 weeks treatment (only for Part 2 at selected sites, if applicable).

#### 2.1.9 Exploratory Objective

NA

## 2.2 Study Type and Design

Study Phase: Ila

**Study Design:** Double-blind, multi-center, two-part, randomized, placebo-controlled study with 4 weeks of treatment with AP1189 in early rheumatoid arthritis (RA)

**Study Flow Chart:** Study flow chart is shown in the study protocol, Table 3, section 20 Schedule of Visits.

## **3 STATISTICAL ANALYSIS CONSIDERATIONS**

## 3.1 Types of Analysis

All safety parameters (ECG, vital signs, AEs/SAEs, laboratory abnormalities, etc.) will be summarized by treatment and time point. Continuous variables will be summarized using n, mean, standard deviation, median, minimum, and maximum values. For categorical (nominal) variables, the number

of patients per category, and percent of the total number of patients will be presented.

Descriptive statistics (continuous and categorical variables summarized as above) will be used for an exploratory description of exposure. Plasma concentrations will be used to measure exposure.

All efficacy endpoints will be evaluated by treatment group using descriptive statistics (continuous and categorical variables summarized as above). Confidence intervals will be presented where appropriate.

### **3.2** Analysis Data Sets

The sets of subjects to be analyzed are defined as follows:

- The safety analysis set consists of all subjects who received the study medication at least once, analyzed by received treatment.
- The **pharmacokinetic (PK) analysis set** consists of all subjects who completed the study and did not have any protocol deviation or events implying a bias for the PK evaluation.
- The efficacy analysis set consists of all randomized subjects who received the study medication at least once, analyzed by randomized treatment (intention to treat). A second analysis of the primary efficacy endpoint, for robustness, will be performed for all randomized subjects who complete the study without any major protocol violations (per protocol).

All safety and tolerability analyses will be conducted on the safety data set, all PK analyses will be conducted on the pharmacokinetic data set, and all efficacy analyses will be conducted on the efficacy data set.

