15 EXPERIMENTAL PLAN

15.1 Study Design

This study is a multicenter, two-part, randomized, double-blind, placebo-controlled, 4-week study with repeated doses of AP1189. The study population will consist of newly diagnosed subjects with severe active RA (CDAI > 22) who are to start up-titration with MTX. A minimum of 90 subjects are expected to complete the study, plus 45 subjects from Bulgaria and/or Moldova for a sub-study (see Section 15.2). Up to 120 subjects are planned to be enrolled for the main study to account for discontinuation rate, and up to 60 subjects for the sub-study. The rationale for the number of subjects required is outlined in the section on sample size determination. The below Figure 1 shows the general study design.

Figure 1.: General study design (Part 1 and 2)

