21.4.1 PK Sample Collection

Plasma PK samples for exposure-response analysis will be taken after 1, 2, 3- and 4-weeks treatment.

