23.1 General Considerations

Before breaking the treatment codes, all decisions on the evaluability of the data from each individual subject will be made and documented, and each subject will be assigned to the appropriate analysis data set. The following analysis sets will be used for the statistical analysis:

Safety: All subjects who received the study medication at least once, analyzed by received

treatment

PK: All the subjects who completed the study and did not have any protocol deviation or events

implying a bias for the PK evaluation

Efficacy: All randomized subjects who received the study medication at least once, analyzed by

randomized treatment (intention to treat). A second analysis of the primary efficacy endpoint, for robustness, will be performed for all randomized subjects who complete the

study without any major protocol violations (per protocol)

A Statistical Analysis Plan (SAP) describing the planned statistical analyses in detail, including interim analyses, will be prepared by CroxxMed, and validated by the sponsor prior to any unblinding of data.

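### The completer-only PK set leaves valid earlier concentrations from withdrawn AP1189 subjects out of the exploratory exposure summary

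*SAP*

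**What the plan says.** SAP 3.2 states that the PK set "consists of all subjects who completed the study and did not have any protocol deviation or events implying a bias for the PK evaluation", and that "all PK analyses will be conducted on the pharmacokinetic data set". Protocol 23.1 gives the same restriction: "All the subjects who completed the study and did not have any protocol deviation or events" of a kind that would bias the PK evaluation. In the same SAP section the safety and efficacy sets require only one dose of study medication.

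On sampling, protocol 21.4.1 says: "Plasma PK samples for exposure-response analysis will be taken after 1, 2, 3- and 4-weeks treatment". SAP 3.12 notes that there is one sample per visit with variable time since the last dose. It therefore drops the exposure-response description and keeps a description of exposure alone.

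On output, SAP 6.2 gives plasma concentrations as a listing. The SAP revision history adds two tables to Appendix 4 in version 2.0: Table 11.4.4.1 (plasma concentrations) and Table 11.4.4.2 (time from last dose to sample). Appendix 4 is a separate document, so any population note on those tables cannot be seen here. SAP 3.2 governs as written.

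Study completion appears in SAP section 4 as a yes/no CRF item (DSSTAT) with no further definition.

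**The concern.** A completer rule makes sense when a PK parameter needs a full set of samples. Nothing here does, because the summary is of single concentrations by visit. Removing a subject's week 1 value because the subject left in week 3 loses usable data and gains no validity. It also sits awkwardly with SAP 3.3, which includes subjects with missing data where possible.

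Completion may also depend on exposure. Protocol 16.5.2 allows withdrawal for medical or safety reasons, and protocol 19.1.1.1 links stopping of study drug to liver enzymes. If people with higher concentrations leave more often, the table describes exposure in a selected remainder and shows nothing of those who left.

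There is a second route to loss. Because completion is only a yes/no item, a subject with all four samples who misses Visit 7 or the follow-up call could be recorded as a non-completer and lose every value.

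**Working it through.** **Inputs**
- Planned completers (protocol 15.1): 90 main study, 45 sub-study. Planned enrolment: up to 120 and up to 60.
- Parts of the main study (protocol 15.3.1, 15.4.1): 24 completers from 32 enrolled, and 66 from 88.
- Allocation (protocol 15.3, 15.4): 2:1 active to placebo in Part 1, and two thirds active under each Part 2 design. The sub-study has a minimum of 15 per group (protocol 23.2.2); 45 = 3 x 15 with two thirds active is assumed.
- Phase 1 steady-state troughs, mean and SD (protocol 11.3.1): 46 and 14 ng/mL at 50 mg; 100 and 25 ng/mL at 100 mg.
- Half-life near 20 h (protocol 10.1.1).

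**Implied non-completion.** 1 - 90/120 = 25%. With N = completers/(1 - 0.25): 90/0.75 = 120, 45/0.75 = 60, 24/0.75 = 32, 66/0.75 = 88. All four planned enrolments are reproduced exactly. The current text states no rate, so 25% is an inference from enrolment ceilings.

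**AP1189 subjects affected.** Enrolled on active: 120 x 2/3 = 80 and 60 x 2/3 = 40, total 120. Completing on active: 8 + 8 + 44 = 60 and 30, total 90. At most 120 - 90 = 30 fall outside the set.

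**Samples from weeks 1 to 3.** The timing of withdrawal is not given, so a range is needed.
- All 30 leave before week 1: 0 samples.
- Withdrawals evenly spread over four weeks (assumption): 30 x (0.75 + 0.50 + 0.25) = 45.
- All leave after week 3: 30 x 3 = 90.
- At an assumed 5% to 20% non-completion with even spread: 6 to 24 subjects and 9 to 36 samples.

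These counts exclude week 4 samples from anyone recorded as a non-completer only for a later missed contact.

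**Extreme bound on selection.** Assume normal troughs and that the highest-exposed quarter all leave. The mean of the lower 75% is mean - SD x 0.3178/0.75.
- 100 mg: 100 - 25 x 0.424 = 89.4 ng/mL (-11%).
- 50 mg: 46 - 14 x 0.424 = 40.1 ng/mL (-13%).
- Mean of the quarter removed at 100 mg: 100 + 25 x 0.3178/0.25 = 131.8 ng/mL.

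If withdrawal is unrelated to exposure, the expected shift is zero.

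**What the fix would recover under that extreme.** With evenly spread withdrawal, the 100 mg means by visit would be:
- week 1: (0.75 x 89.4 + 0.1875 x 131.8)/0.9375 = 97.9 ng/mL;
- week 2: (0.75 x 89.4 + 0.125 x 131.8)/0.875 = 95.5 ng/mL;
- week 3: (0.75 x 89.4 + 0.0625 x 131.8)/0.8125 = 92.7 ng/mL;
- week 4: 89.4 ng/mL, unchanged.

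The completer-only table would show 89.4 ng/mL at every visit.

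**Scale against sampling time.** With a 20 h half-life, a fall from 100 to 89.4 equals 20 x ln(100/89.4)/ln 2 = 3.2 h of later sampling. A fall from 46 to 40.1 equals about 4 h.

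**The case against.** The strongest reply is that little depends on this set. Protocol and SAP agree with each other, the output is exploratory, and SAP 3.12 has already given up relating exposure to effect. Sampling-time variation of three to four hours could move a mean as far as the extreme selection bound. All of this stands and limits the importance of the point. It is not a reason to leave out valid data.

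The deviation clause can also be defended. It removes only deviations or events that would bias the PK evaluation, and protocol 23.1 has evaluability decided before the codes are broken. That stands too; the difficulty is that it acts on subjects where acting on samples would do.

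A reader might infer more than the documents support:
- That exposure is described only in people who tolerated the drug. SAP section 4 also lists subject choice, investigator choice, non-compliance and other reasons for not completing. Protocol 19.1.1.1 lets study drug be paused and resumed, so a subject with a liver-enzyme rise can complete. Protocol 16.5.2 separates leaving treatment from leaving the study.
- That every withdrawn subject's data are discarded. Someone who leaves before week 1 has no sample to lose, and the SAP 6.2 listing is not tied to the PK set.
- That a quarter of all subjects lose exposure data. The overall proportion includes placebo subjects, who have no AP1189 exposure to describe.
- That the mean is biased by 11% or 13%. In phase 1 Part IV (protocol 10.1.6), the possibly related events arose in one subject at 50 mg and one at 200 mg. The aminotransferase rises were confined to the 200 mg cohort and included two placebo subjects. Protocol 26.2 reports no treatment discontinuation from gastrointestinal effects. Exposure-driven dropout at 50 or 100 mg is therefore an assumption.

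**Conclusion.** The point holds as a modest one. The completer rule leaves out of the exposure summary the valid concentrations of AP1189 subjects who withdraw after week 1. It may also leave out those of subjects with all four samples who miss a later contact. At most about 30 of 120 AP1189 subjects are affected, with roughly 45 samples from weeks 1 to 3 (range 0 to 90). This rests on the 25% implied by the enrolment ceilings and on an assumed even spread of withdrawals.

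Whether the summary is biased depends on whether withdrawal is related to exposure, which the documents do not settle. The shifts of -11% at 100 mg and -13% at 50 mg are a hypothetical extreme and apply only to visits before withdrawal. Efficacy and safety analyses use their own sets and are untouched.

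**What to change.** In SAP 3.2, define the PK set as all subjects who received at least one dose of AP1189 and have at least one evaluable concentration with known sampling time and last-dose time, analysed by treatment received. Record the departure from protocol 23.1 in SAP 3.12.

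Exclude individual samples affected by a PK-relevant deviation or a dose interruption, not whole subjects. Show the completer-only version of Table 11.4.4.1 as a sensitivity table, and state which set the SAP 6.2 listing uses.

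The samples are already part of the plan, and Table 11.4.4.2 already calls for the time since last dose, so no new data are needed. The cost is the wording, slightly more analysis work and one extra descriptive table. The change cannot recover samples never taken after withdrawal, so later visits would still describe only those who remained.

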#### 3.3 Measurement Times, Missing Data, and Outliers

#### Measurement Times

The first date registered (screening visit) is to be used to define Baseline visit (Week 0 visit, within 14 days from screening). Week 1 visit is defined to be 7 days (±1 day) after Baseline, Week 2 visit 14 days (±1 day) after Baseline, Week 3 visit 21 days (±1 day) after Baseline, Week 4 visit 28 days (±1 day) after Baseline, final visit 7 (±2) days after the last investigational medicinal product has been taken, and visit 8 (end of study follow-up call) 4 weeks (±3 days) after the last investigational medicinal product has been taken, as described in protocol section 20.1. Any dates outside these visit windows are noted by the Data Manager during data validation as protocol deviations.

#### Missing Data

Subjects with missing data will be included where possible, e.g. in the description of the patient population. Wherever the analysis requires data on a variable, subjects with missing data on that variable will be excluded from the analysis (e.g. when calculating changes from baseline). Missing items will not be imputed in any way, however plasma concentration values below the level of quantification will be set to LoQ/2 for the pharmacokinetic analysis.

#### **Outliers**

No procedure for dealing with outliers was foreseen in the trial protocol and therefore one analysis with the actual values and at least one other analysis eliminating or reducing the outlier effect will be performed and differences between their results will be discussed.

## **3.4 Prognostic Variables**

NA

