15.3 Part 1 (main study only)

Following a successful screening evaluation, subjects who fulfill the enrollment criteria will be randomized in a 2:1 ratio in group A and B. One group will receive active treatment, and the other group will receive a placebo. Before randomization into group C/D (the same 2:1 ratio between active and placebo), the SC will look at blinded safety data from group A/B.

- Group A (min. 8 subjects): AP1189 dose 50 mg, once daily for 4 weeks (28 days) plus MTX (10-25 mg) weekly
- Group B (min. 4 subjects): placebo for 4 weeks (28 days) plus MTX (10-25 mg) weekly

SC Meeting

- Group C (min. 8 subjects): AP1189 dose 100 mg, once daily for 4 weeks (28 days) plus MTX (10-25 mg) weekly
- Group D (min. 4 subjects): placebo for 4 weeks (28 days) plus MTX (10-25 mg) weekly

Protocol Code Number: SynAct-CS002

15.3.1 Number of Subjects in Part 1

A minimum of 24 subjects is expected to complete Part 1 of the study. About 32 subjects are planned to be enrolled in accounting for discontinuation rate.

The rationale for the number of subjects required is outlined in the section on sample size determination.

15.4 Part 2

All subjects will be randomized into one design only, either design 1, 2, or 3 based on data from the interim analysis:

- Design 1: AP1189 dose 50 mg (min. 44 subjects) or placebo (min. 22 subjects), once daily for 4 weeks (28 days) plus MTX (10-25 mg) weekly
- Design 2: AP1189 dose 100 mg (min. 44 subjects) or placebo (min. 22 subjects), once daily for 4 weeks (28 days) plus MTX (10-25 mg) weekly
- Design 3: Continue with the same doses as in Part 1, in a 1:1:1 ratio (AP1189 50 mg (min. 22 subjects), AP1189 100 mg (min. 22 subjects) or placebo (min. 22 subjects)) plus MTX (10-25 mg) weekly

Following a successful screening evaluation, subjects who fulfill the enrollment criteria will be randomized accordingly.

15.4.1 Number of Subjects in Part 2

A minimum of 66 subjects in the main study is expected to complete Part 2 of the study, and 45 subjects in the sub-study. About 88 subjects are planned to be enrolled in the main study in accounting for discontinuation rate, and about 60 subjects in the sub-study.

The rationale for the number of subjects required is outlined in the section on sample size determination.

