23.2 Determination of Sample Size

Calculations of sample size are based on a 95% confidence interval for the mean change in CDAI from baseline.

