23.2.1 Main study

For a sample size of 25 subjects, and a standard deviation for the mean change of 3 points, a 95% confidence interval will be around 2.8 points wide with 80% probability. This interval width provides a good precision of the estimate of the primary efficacy endpoint. For a sample size of 30 subjects, the interval will be around 2.5 points wide, which provides even better precision. If the sample size is larger, or if the standard deviation is smaller, the interval will be shorter (i.e., the precision will be higher). A larger standard deviation than 3 points is unlikely. SAS proc power is used for the calculations.

The study is designed to provide a minimum of 30 subjects in each of the treatment groups that proceed to Part 2, and a total of 90 patients.

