## 3.5 Subgroup Analyses

A sub-study taking place in Bulgaria and Moldova was added to the clinical study protocol. The substudy was added to investigate if the effect of AP1189 in newly diagnosed subjects with severe RA who are to start up-titration with methotrexate is comparable in these two countries compared to the main study. In addition to analyzing the main study and the sub-study separately, all data will be pooled to investigate the overall effect in all participating countries.

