#### 6.1.1 Description of primary efficacy variables

| Variable (CRF annotation)   | How to be presented                                    |
|---|--|
| Patient Global Assessment of Disease Activity RA,
cm (PGADA, dataset CDAI)                                   | n, mean (95% CI), sd, median, min, max, by
visit    |
| Patient Global Assessment of Disease Activity RA,
cm, relative to placebo (derived, see Section 3.6)         | Mean, median, min, max, by visit, country, and site    |
| Investigator Global Assessment of Disease
Activity RA, cm (IGADA, dataset CDAI)                              | n, mean (95% CI), sd, median, min, max, by
visit    |
| Investigator Global Assessment of Disease
Activity RA, cm, relative to placebo (derived, see
Section 3.6) | mean, median, min, max, by visit, country,
and site |
| CDAI score calculated (CDAI)  | n, mean (95% CI), sd, median, min, max, by visit       |

Study SynAct-CS002 – Statistical Analysis Plan

| CDAI score calculated, relative to placebo (derived, see Section 3.6)  | Mean, median, min, max, by visit, country, and site          |
|--|--|
| CDAI change from baseline to week 4 (derived, see Section 3.6)   | n, mean (95% CI), sd, median, min, max, by
visit          |
| Proportion of subjects with a change in CDAI
score from severe (CDAI > 22) to moderate or
lower (CDAI ≤ 22) at week 4 compared to
baseline (derived, see Section 3.6) | <pre># patients and % /category (2 categories: Yes/No)</pre> |

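### With no prognostic variables named, CDAI change is set against placebo without adjustment for baseline CDAI, and 4 of 30 placebo subjects per dose appear to be non-concurrent

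*SAP*

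**What the plan says.** **Analysis.** SAP section "3.4 Prognostic Variables" has the single entry NA. SAP 3.1 adds: "All efficacy endpoints will be evaluated by treatment group using descriptive statistics". The first primary variable in SAP 2.1.4 is "Mean change in CDAI from baseline to week 4". SAP 6.1.1 lists "CDAI change from baseline to week 4" with n, mean (95% CI), SD, median, minimum and maximum, and the response from CDAI > 22 to ≤ 22 as counts and percentages. The placebo comparison takes the form of ratios: SAP 3.6 divides each active group's CDAI score summaries by the placebo group's, and SAP 3.8 gives values relative to placebo by country and site. No term or stratum for baseline CDAI, Part or randomisation cohort appears in these analyses.

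**Design.** In Part 1 (Protocol 15.3) subjects "will be randomized in a 2:1 ratio in group A and B": at least 8 on 50 mg and 4 on placebo. After a blinded Steering Committee review, a second 2:1 randomisation gives groups C and D: at least 8 on 100 mg and 4 on placebo. Part 2 is 22/22/22 under Design 3, or 44 active and 22 placebo under Designs 1 and 2.

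**Size.** Protocol 23.2 states: "Calculations of sample size are based on a 95% confidence interval for the mean change in CDAI from baseline". Protocol 23.2.1 aims for "a minimum of 30 subjects in each of the treatment groups that proceed to Part 2", and 90 in total. SAP 3.5 analyses the main study and the Bulgaria/Moldova sub-study separately, and then "all data will be pooled to investigate the overall effect in all participating countries".

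**The concern.** The primary efficacy objective is AP1189 versus placebo, so the arm means will be read against each other.

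Baseline CDAI matters to that reading. A subject who enters at 23 needs a 1-point fall to reach 22; one who enters at 40 needs 18. With about 30 per arm, a chance imbalance at baseline passes straight into both primary variables, and nothing planned removes it.

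The second issue is who the placebo subjects are. Placebo reaches 30 only as 4 + 4 + 22, so each dose is compared partly with placebo subjects randomised against the other dose at a different time. If the two Part 1 cohorts differ in mean CDAI change for reasons unrelated to treatment, part of that gap enters the single-dose comparison.

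**Working it through.** **1. The plan's own figures.** Width reached with 80% probability = 2 × t(0.975, n−1) × SD/√n × √[χ²(0.80, n−1)/(n−1)].

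| n | SD | Stated width | Recomputed |
|---|---|---|---|
| 25 | 3 | 2.8 | 2.75 |
| 30 | 3 | 2.5 | 2.47 |
| 15 | 2.5 | 3.2 | 3.15 |

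They reproduce to rounding. All are one-arm widths. For a difference of 30 versus 30 at SD 3, SE = 3 × √(1/30 + 1/30) = 0.775, and the 95% interval is 3.10 points wide.

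**2. Gain from baseline CDAI.** Let r be the baseline/week-4 correlation and k the baseline SD divided by the week-4 SD. Both are assumed, since the documents give neither.

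Variance ratio, adjusted to raw change = (1 − r²)/(1 + k² − 2rk). With k = 1 this is (1 + r)/2.

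| r | k | Variance ratio | Interval narrower by |
|---|---|---|---|
| 0.3 | 1 | 0.65 | 19% |
| 0.5 | 1 | 0.75 | 13% |
| 0.7 | 1 | 0.85 | 8% |
| 0.5 | 0.7 | 0.75/0.79 = 0.95 | 3% |
| any | k = r | 1.00 | 0% |

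At r = 0.5 and k = 1 the 3.10-point interval becomes 3.10 × 0.866 = 2.7 points, and 30 per arm performs like 30/0.75 = 40. Entry is cut at CDAI > 22, which may make k less than 1.

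**3. Non-concurrent placebo under Design 3 (minimum counts).**
- 50 mg arm: 8/30 from A/B, 22/30 from Part 2.
- Placebo arm: 4/30 from A/B, 4/30 from C/D, 22/30 from Part 2.
- Raw contrast: +4/30 of the A/B level, −4/30 of the C/D level, 0 of Part 2. For 100 mg the signs reverse.

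Bias = 4/30 × gap = 0.133 × gap. For assumed gaps of 3 and 5 points this is 0.40 and 0.67 points, against a half-width of 3.10/2 = 1.55. With the sub-study pooled the weight is 4/45 = 0.089, giving 0.27 and 0.44. With both doses pooled, the shares are 8/60 = 4/30 in each Part 1 cohort and 44/60 = 22/30 in Part 2, so the bias is zero.

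Under Designs 1 or 2 the retained dose has weights −4/30 = −0.133 on the other dose's cohort, 8/52 − 4/30 = +0.021 on its own, and 44/52 − 22/30 = +0.113 on Part 2.

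**4. Cost of a cohort term.** Least squares on the Design 3 counts gives SE 0.775 without and 0.795 with cohort, a variance ratio of 1.054.

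**5. Overall pooled display.** With 90 main-study and 45 sub-study subjects, SD 3 in each, and an assumed gap d in mean change, the unstratified SD is √(9 + (2/3)(1/3)d²): 3.32 at d = 3 and 3.82 at d = 5. If the sub-study is allocated equally, 15 per group, this adds spread and not bias.

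**The case against.** The strongest defence is that the plan is descriptive: per-arm summaries, sized on one-arm interval width, with no between-arm estimate for a covariate to sharpen. CDAI by visit would show a baseline imbalance, and SAP Appendix 5 lists a table for the quarter of subjects with the highest baseline CDAI. This does not settle the matter. The objective is a comparison with placebo and the SAP tabulates values relative to placebo. It does show that a covariate list alone is not enough; the SAP also needs a between-arm estimate.

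Several stronger readings are tempting and are not supported:

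- *Nothing separates the cohorts.* Main study and sub-study are analysed separately, and primary endpoints are shown by country and site. Only A/B, C/D and Part 2 are left undivided, so the SD inflation in step 5 touches the overall display alone.
- *Changing allocation ratios distort the result.* Ratios differ only under Design 3, where Part 1 supplies 8/30 of every arm and a Part 1 to Part 2 shift cancels. The unequal shares 8/52 and 8/30 arise only under Designs 1 and 2, where every cohort is 2:1. The two cannot be combined.
- *Leaving out cohort loses precision in the main study.* It risks bias; adding the term costs about 5% in variance.
- *An 8 to 19% gain is assured.* It requires equal SDs, and the range starts at zero.

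It also stands that merging Parts 1 and 2 is inferred from the counts of 30 and 90; the SAP does not state it.

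**Conclusion.** The point holds in moderate form. Leaving baseline CDAI out forgoes an adjustment that uses data already collected and can cost no more precision than a degree of freedom. The gain for the difference runs from none to 19%, depending on r and k. The non-concurrent placebo is a small, conditional problem: 4 of 30 subjects per dose, with a possible bias of 0.4 to 0.67 points under Design 3 in the main study. The assumed gaps of 3 to 5 points are at least one planned SD, so these figures are illustrations and not forecasts. The bias is zero for the pooled-dose contrast under Design 3. The documents do not name the design chosen; a 45-subject sub-study with 15 per group implies three groups, which points to Design 3. The stated sample-size figures are unaffected.

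**What to change.** Replace NA in SAP 3.4 with a linear model for CDAI change at week 4 containing treatment and baseline CDAI, plus a main/sub-study term in the overall pooled analysis. Report adjusted means and the active-minus-placebo difference with 95% CI, and keep the raw means alongside. State explicitly whether Parts 1 and 2 are combined. Keep the separate main and sub-study analyses, because an additive model assumes a common treatment effect and Protocol 23.2.2 expects a smaller one in the sub-study.

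Add a sensitivity analysis that either includes randomisation cohort (A/B, C/D, Part 2) or uses concurrent placebo only. The cohort term costs about 5% more variance. If concurrent placebo is used under Design 3, compare within Part: 8/30 of the 50 mg arm but 4/26 of its concurrent placebo would come from A/B.

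Standardise the responder proportion over baseline CDAI. It cannot be standardised over the Part 1 cohorts, since A/B has no 100 mg subjects and C/D has no 50 mg subjects.

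The cost is SAP wording and one model with its sensitivity run; no new data are needed.
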